| Study Design | Single center, mechanistic study in which healthy subjects will be will be stratified by age in 22 subjects (ages 25-40) and 66 subjects (ages 60-89) and randomized to receive PPV23 or PCV13 in 1:1 ratio. Blood samples will be collected on Days D0 (at enrollment) and D1, D3, D7, D14, D30, D180 and year 2-3.5 post vaccination to study innate and adaptive immune responses. Recording and reporting safety data will be as follows: Any Adverse Event (including – but not only- vaccine reactions and local or systemic Reactogenicity Events) of grade 3 or higher severity or serious adverse event (SAE) occurring after vaccination while the subjects is still at the clinical site. Local REs evaluation of grade 3 or higher severity occurring from Day 0 to Day 7 reported over the telephone by the participant and/or assessed at the clinic. AEs of grade 3 or higher severity throughout D180 of the study (including -but not only – AEs linked to blood draws). All SAEs throughout D180. |
| Primary Endpoints | Identification of generic innate immune signatures [Traditional immune parameters measurements + array-based gene expression] at days 1, 3 and 7 post vaccination with either PPV23 or PCV13 in the elderly. Measurement of adaptive immune responses [Opsonophagocytosis assay (OPA) titers] at day 30 post vaccination with either PPV23 or PCV13 in the elderly. Correlation of signatures of generic innate immune responses at days 1, 3 and 7 with adaptive immune responses [Opsonophagocytosis assay OPA titers] at day 30 post vaccination with either PPV23 or PCV13 in the elderly. |
| Secondary Endpoints | Comparison of the serotype-specific IgG levels at day 30 post vaccination with either PPV23 or PCV13 in the elderly. Correlation of signatures of generic innate immune responses at days 1, 3 and 7 with serotype specific IgG levels at day 30 post vaccination with either PPV23 or PCV13 in the elderly. Comparison of the serotype-specific avidity indexes in a subset |

| | of up to 6 vaccinees per vaccine group at day 180 post vaccination with either PPV23 or PCV13 in the elderly. 4. Correlation of signatures of generic innate immune responses at days 1, 3 and 7 with serotype specific avidity indexes in a subset of vaccinees at day 180 post vaccination with either PPV23 or PCV13 in the elderly. 5. Comparison of the adaptive immune responses [Opsonophagocytosis assay (OPA) titers] at day 30 post vaccination with either PPV23 or PCV13 in the elderly. |

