1.7 Benefits

1.7.1 Benefits of Investigational Product(s)/Intervention(s)

Participants will have the benefit of receiving a licensed pneumococcal vaccine which may offer protection against pneumococcal disease. Also the knowledge gained from this study could facilitate the design of more effective pneumococcal vaccines for the geriatric population.

1.7.2 Benefits of Study Procedure(s)

None

2. **OBJECTIVES**

PCV13 induces better functional immune responses when compared to PPV23 in older naïve adults. We hypothesize that this is due to intrinsic defects in innate responses that could explain the poor immunogenicity of PPV23 when compared to PCV13. Therefore, we propose to extensively study innate and adaptive immune responses generated after administration of either pneumococcal polysaccharide or conjugate vaccines in older adults.

2.1 **Primary Objective(s)**

To analyze the generic innate immune signatures that correlate with the magnitude of the adaptive immune responses (opsonophagocytosis [OPA] titers) at day 30 in order to identify the correlation signatures of the innate immune responses to PPV23 and PCV13.

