3.1 Study Endpoints

3.1.1 Primary Endpoint(s)

- 3.1.1.1 Identification of generic innate immune signatures [Traditional immune parameters measurements + array-based gene expression] at days 1, 3 and 7 post vaccination with either PPV23 or PCV13 in the elderly.
- 3.1.1.2. Measurement of adaptive immune responses [Opsonophagocytosis assay (OPA) titers] at day 30 post vaccination with either PPV23 or PCV13 in the elderly.
- 3.1.1.3. Correlation of signatures of generic innate immune responses at days 1, 3 and 7 with adaptive immune responses [Opsonophagocytosis assay OPA titers] at day 30 post vaccination with either PPV23 or PCV13 in the elderly.

3.1.2 Secondary Endpoint(s)

- 3.1.2.1. Comparison of serotype specific IgG levels at day 30 post vaccination with either PPV23 or PCV13 in the elderly.
- 3.1.2.2. Correlation of signatures of generic innate immune responses at days 1, 3 and 7 that correlate to serotype specific IgG levels at day 30 post vaccination with either PPV23 or PCV13 in the elderly.
- 3.1.2.3. Comparison of the serotype specific avidity indexes in a subset of up to 6 vaccinees per vaccine group at day180 post vaccination with either PPV23 or PCV13 in the elderly.

- 3.1.2.4. Correlation signatures of generic innate immune responses at days 1, 3 and 7 that correlate to serotype specific avidity indexes in a subset of up to 6 vaccinees per vaccine group at day 180 post vaccination with either PPV23 or PCV13 in the elderly.
- 3.1.2.5. Comparison of the adaptive immune responses [Opsonophagocytosis assay (OPA) titers] at day 30 post vaccination with either PPV23 or PCV13 in the elderly.

3.1.3 Exploratory Endpoint(s)

3.1.3.1. Identification of correlation signatures of generic innate immune responses at days 1, 3 and 7 that correlate to adaptive immune responses [Opsonophagocytosis assay OPA titers specifically] at day 30 post vaccination among subjects in different age strata.

3.1.3.2. Comparison of the kinetics and magnitude of select serotype specific plasmablasts (days 7, 14, 30(with day 30 on a subset of vaccinees only)) and memory B cells (days 30, 180) post vaccination with either PPV23 or PCV13.

3.1.3.3. Comparison of the repertoire and monoclonal antibodies from plasmablasts in a subset of vaccinees per vaccine group at day 7 post vaccination with either PPV23 or PCV13.

3.1.3.4. Comparison of identified innate signature variables and correlation signature variables between PPV23 and PCV13 recipients.

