9.2. Data Analysis

9.2.1. General considerations

The young treatment groups are of limited size. The main purpose of the young treatment groups is to provide some indication whether the elderly respond to the vaccines differently than the young. By themselves, the young groups do not have sufficient statistical power to generate reliable innate and correlation signatures. However when used in comparison against elderly groups, and by only considering biological pathways (collections of genes contributing to the same biological process) that are affected by the vaccine, they can provide some indication as to how different the response is in the elderly compared to the young. Thus for data analysis, the young treatment groups will be used only in exploratory endpoints. The primary and secondary endpoints will focus on the elderly groups.

The analyses will be based on population with critical time points met, defined as those who received vaccine per label and got the 4 draws required for the primary endpoint, i.e. draws at days 1, 3, 7 (\pm 1), and 30 (\pm 7) within the required windows. Data from the study will be analyzed using the statistical software R³¹. High-throughput data will be analyzed using appropriate methods, either by stand-alone software or modules in leading statistical softwares, e.g. the Bioconductor in the R framework³². For cytokine data, missing values will be dealt with using multiple imputations. For microarray data, nearest neighbor method and local least squares may be used to fill missing values. Unsupervised learning techniques such as PCA, PLSDA, clustering, and factor analysis ³³ will be used for the visualization and identification of global patterns. For descriptive endpoint (primary endpoint 2), we will generate summary statistics, and visualize the data using histograms and boxplots when applicable. For the identification of innate signatures, the two treatment groups will be analyzed separately.

Analyses of primary endpoints:

1. Identification of generic innate immune signatures [Traditional immune parameters measurements + array-based gene expression] at days 1, 3 and 7 post vaccination with either PPV23 or PCV13 in the elderly.

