4. Correlation of signatures of generic innate immune responses at days 1, 3 and 7 with serotype specific avidity indexes in a subset of up to 6 vaccinees per vaccine group at day 180 post vaccination with either PPV23 or PCV13 in the elderly.

The analysis will be conducted in each elderly treatment group separately. For traditional immune parameters, we will calculate the correlation coefficient between the immune parameter and the adaptive immune response (serotype specific avidity indexes at day 180 p) the p-values associated with the correlation coefficients will be used to select traditional immune parameters that are associated with the respective adaptive immune responses (serotype specific avidity indexes at day 180). The tentative selection criterion is p-value ≤ 0.01 .

For gene expression data, we will use the method Significance Analysis of Microarrays (SAM) with quantitative outcome to identify genes that are significantly associated with the respective adaptive immune responses (serotype specific avidity indexes at day 180). False discovery rate (FDR) will be used as selection criterion. The tentative selection criterion is $FDR \le 0.1$.

5. Comparison of the adaptive immune responses [Opsonophagocytosis assay (OPA) titers] at day 30 post vaccination with either PPV23 or PCV13 in the elderly.

Descriptive analysis, boxpots and histograms, will be conducted to present and visually contrast the data. Testing between the two elderly treatment groups will be conducted using unpaired t-test after proper data transformation. In the case that near-normality cannot be achieved with data transformation, we will resort to the Wilcoxon test.

Analyses of exploratory endpoints

1. Correlation of signatures of generic innate immune responses at days 1, 3 and 7 with adaptive immune responses [Opsonophagocytosis assay OPA titers specifically] at day 30 post vaccination among subjects in different age strata

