For all endpoints, our data analysis will be based on all subjects who are randomized, receive vaccination per label, and for whom there is a blood sample taken at the 2 required time points (Day 0 and Day 30 + 7 - 7 days) and or Day 0 and Day 180.

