Appendix 1. Schedule of Events

| Day or Year | 0 | 1 | 3 | 7 +/-1 | 14 +/-2 | 30 +/-7 | 180 +/- 14 | 2-3.5 |
|--|---|---|---|-----------|------------|------------|------------------|-------|
| Visit | 1 | 2 | 3 | 4 | 5 | 6 | 7 | 8 |
| Informed consent & HIPAA | Х | | | | | | | |
| Demographic and Medical History (including medication and vaccine history). | Х | | | | | | | |
| Verify eligibility | Х | | | | | | | |
| PID assignment | Х | | | | | | | |
| Vital signs | Х | | | | | | | |
| Focused physical exam (only if indicated based on review of health status) | Х | Х | X | X | X | X | X | Х |
| Randomization | Х | | | | | | | |
| Vaccination* | Х | | | | | | | |
| Urine Pregnancy Test **** | Х | | | | | | | |
| Record additional pneumococcal vaccines given outside study | | | | | | | | Х |
| ** Instruction given to study participants on immediate notification of safety events and concomitant medications. | Х | Х | х | х | Х | х | | |
| Assessment of health status *** and concomitant medications after administration of study vaccine | | х | х | x | х | Х | х | X**** |
| Blood draw for Innate Assays (microarray, FACS, Luminex) and Adaptive Assays (Plasmablasts, monoclonal Ab, memory B cells, serotype specific ELISA IgG levels, avidity assay, OPA) **** | Х | Х | Х | Х | X | X | x | Х |

Footnotes:

* Any Adverse Event (including – but not only- vaccine reactions and local or systemic Reactogenicity Events) of grade 3 or higher severity or serious adverse event (SAE) occurring after vaccination while the subjects is still at the clinical site will be recorded and reported.

** Instruction includes the following:

1. Participants will be provided (on Day 0 only) with a written description of what represents a local and systemic vaccine reaction of mild, moderate and severe intensity and instructed to call the site to report reactogencity events of grade 3 (severe) or higher severity within 1 week following vaccination.

2. Participants will also be instructed to promptly call the site if he/she develops any of the following:

- Becomes sick or has been treated at the doctor's office or emergency department or has been hospitalized for any illness throughout D180 of the study;
- Develops any adverse event that limits self-care activities of daily living (e.g. bathing, dressing and undressing, feeding self, using the toilet, taking medications, and not bed ridden) even if he/she decides not to get medical care; or

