- he/she starts/stops medications during enrollment in the study.
- Becomes pregnant.

*** Assessment of health status includes:

- Evaluation of local REs and systemic REs of grade 3 or higher severity developing after the last visit (only until Day 7 Visit)
- Any adverse event (AE) that limited self-care activities of daily living or any serious adverse event (SAE) which may not have been reported by the participant by calling the site as directed at a prior visit
- Any medications administered after vaccination.

**** Innate assays will not be conducted at days 30 and 180. Adaptive assays will not be conducted at day 1.

***** Eligible female subjects aged 25-40 years will use effective contraception 1 month prior and one month following vaccination.

***** Only for major health problems

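### Secondary 1 and 5 compare day-30 IgG and OPA between the elderly arms without using the day-0 antibody value: a valid test that may give up precision

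*Combined protocol and SAP*

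**What the plan says.** Section 9.2.1 gives the same test for Secondary 1 and Secondary 5: "Testing between the two elderly treatment groups will be conducted using unpaired t-test after proper data transformation". If a transformation does not bring the data near normality, the Wilcoxon test is used. Neither analysis names a day-0 value, a change from baseline or any covariate. The section sets a baseline only for the innate parameters and genes of Primary 1.

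Several places bear on whether a day-0 antibody value will exist:

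- Synopsis, Study Design: blood is collected "on Days D0 (at enrollment) and D1, D3, D7, D14, D30, D180 and year 2-3.5 post vaccination to study innate and adaptive immune responses".
- Appendix 1: one blood-draw row, crossed at day 0, covers the innate assays and "Adaptive Assays (Plasmablasts, monoclonal Ab, memory B cells, serotype specific ELISA IgG levels, avidity assay, OPA".
- Appendix 1, footnote to that row: "Innate assays will not be conducted at days 30 and 180. Adaptive assays will not be conducted at day 1".
- Section 9.2.2: the analysis set is limited to participants "for whom there is a blood sample taken at the 2 required time points (Day 0 and Day 30", with day 0 and day 180 as the alternative.
- Section 9.2.1, General considerations: the population is instead "defined as those who received vaccine per label and got the 4 draws required for the primary endpoint", namely days 1, 3, 7 and 30. Day 0 is not listed.

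**The concern.** In a randomised comparison of a post-vaccination antibody level, the participant's own pre-vaccination level is the obvious covariate. If it predicts the day-30 level within arm, leaving it out keeps explainable variation in the error term, so only larger vaccine differences can be detected with the same roughly 60 elderly participants.

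Chance imbalance also passes into the contrast. At 30 per arm, the difference in mean day-0 log titre has a standard error of sqrt(2/30) = 0.26 SD. At a day-0/day-30 correlation of 0.5, one such standard error moves the unadjusted day-30 contrast by about 0.5 × 0.26 = 0.13 SD.

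The trial's rationale is that PCV13 induces better functional responses than PPV23 in older adults. Secondary 5 is where the trial tests that premise on its own data.

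**Working it through.** **Inputs.** There are 66 elderly participants randomised 1:1 (section 3) with 10% attrition (section 9.1). 66 × 0.9 = 59.4, or 29.7 per arm, and section 9.1 works with 30. The documents state neither an alpha for Secondary 1 and 5 nor a day-0/day-30 correlation. I assume a two-sided alpha of 0.05 and a range for ρ, the within-arm correlation of log day-0 with log day-30 values.

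**The plan's own figures.** Section 9.1 states no power for Secondary 1 or 5. Its nearest figure is 80% power for a paired t-test with n = 30, effect size 0.66 and alpha 0.01. The noncentrality is 0.66 × sqrt(30) = 3.61 on 29 df, which gives 79.7%. The figure reproduces, so I take n = 30 from it.

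**Planned t-test.** The noncentrality is d × sqrt(n/2) on 2n − 2 = 58 df. Power is 80% at d = 0.736 SD, where the noncentrality is 0.736 × sqrt(15) = 2.85.

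**ANCOVA.** Relative to the t-test, the expected variance of the arm contrast is

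(1 − ρ²) × [1 + 1/(2n − 4)] = (1 − ρ²) × 1.018 at n = 30.

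The bracket is the cost of estimating the slope. Power uses noncentrality 2.85 / sqrt(variance ratio) on 2n − 3 = 57 df.

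| Assumed ρ | Variance ratio | Change in SE | Power at 0.736 SD | Difference detectable with 80% power |
|---|---|---|---|---|
| 0 | 1.018 | +0.9% | 79.3% | 0.742 SD |
| 0.2 | 0.977 | −1.1% | 80.9% | 0.727 SD |
| 0.3 | 0.926 | −3.8% | 82.9% | 0.708 SD |
| 0.5 | 0.763 | −12.6% | 89.4% | 0.643 SD |
| 0.7 | 0.519 | −28.0% | 97.3% | 0.530 SD |

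Example at ρ = 0.5: 0.75 × 1.018 = 0.763; sqrt(0.763) = 0.874; 2.85 / 0.874 = 3.26; power 89.4%. In variance terms this equals 30 / 0.763 = 39 per arm with the t-test.

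Simulation with 100,000 trials per value gave ANCOVA power of 79.3%, 82.9%, 89.5% and 97.4% at ρ = 0, 0.3, 0.5 and 0.7, with type I error of 4.9% to 5.1%.

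**Break-even.** Setting the variance ratio to 1 gives ρ = sqrt(1/(2n − 3)) = sqrt(1/57) = 0.13. At that point the two tests are equal.

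**Fold rise as an alternative.** With equal SDs at both days, a change score has variance ratio 2(1 − ρ), which exceeds 1 whenever ρ is below 0.5. Simulated power at 0.736 SD was 50.8%, 66.0%, 79.9% and 95.1% at ρ = 0, 0.3, 0.5 and 0.7. It never beats ANCOVA over this range and is worse than the planned test below 0.5.

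**Is there a day-0 titre?** The Appendix 1 footnote prunes the combined row: it removes innate assays at days 30 and 180 and adaptive assays at day 1, but not adaptive assays at day 0. With the Synopsis and section 9.2.2, this points to day-0 OPA and IgG. It is not proof. The same row also marks assays at visits where the endpoints do not place them: section 3.1.3.2 asks for "select serotype specific plasmablasts (days 7, 14, 30(with day 30 on a subset of vaccinees only", and avidity is an endpoint only at day 180. No sentence says that OPA and IgG are run on day-0 serum.

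**The case against.** The strongest reply is that nothing here is an error. An unpaired t-test between randomised arms is valid, no stated figure is wrong, the study calls itself explorative, and its primary objective concerns correlation signatures rather than a vaccine contrast. The benefit depends on two things that the documents do not settle: whether day-0 serology is run, and how strongly it correlates with day 30. Section 9.4 also leaves room for alternative analyses.

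Most of this stands and limits the point to efficiency. What does not stand is the appeal to section 9.4. Its alternatives are ad hoc, and a covariate chosen after the data are seen is not a prespecified adjustment.

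A reader might infer more than the documents support:

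- *That the arm comparison is biased.* It is not, because the arms are randomised.
- *That any correlation above 0.13 means a real loss.* That value is only break-even. At 0.2 the standard error changes by about 1%.
- *That the Primary 3 and Secondary 2 correlations are wrong for lack of day-0 adjustment.* Section 2.1 asks for signatures that "correlate with the magnitude of the adaptive immune responses (opsonophagocytosis [OPA] titers) at day 30". The attained titre is therefore the target, and a marker linked to prior antibody that truly correlates with it is a true positive under the plan's null.
- *That markers losing significance after adjustment merely reflect prior antibody.* Take a marginal r of 0.57, a marker/day-0 correlation of 0.5 and ρ = 0.5. The true partial correlation is (0.57 − 0.25)/0.75 = 0.43, yet in simulation at n = 30 and alpha 0.01 about half of the selected markers lost significance. At ρ = 0.7 (true partial 0.36) it was 69%. Such a flag would mislead.

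**Conclusion.** The point holds as one of lost precision in Secondary 1 and 5 only. At 30 per arm, day-0 adjustment costs under 1 point of power if the correlation is zero. It gains about 3 points at 0.3, 9 at 0.5 and 17 at 0.7, from a base of 80% at 0.736 SD. The gain is material from a correlation of about 0.3 to 0.5 upwards and negligible below that.

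This rests on an assumed two-sided alpha of 0.05, near-normal log values with a common slope, an assumed correlation that may differ by serotype and assay, and day-0 serology that is inferred rather than stated.

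**What to change.** 1. Confirm that OPA and IgG are assayed on day-0 serum, and say so in the protocol.
2. If they are, make the Secondary 1 and 5 test an ANCOVA of the log day-30 value on arm, with the log day-0 value of the same serotype as covariate. Use a rank-based ANCOVA if near-normality fails. Do not substitute a fold-rise test.
3. Require a day-0 sample for these analyses, as section 9.2.2 does and the population in section 9.2.1 does not. Few exclusions should follow, since section 7.3 has blood drawn at the baseline visit.
4. Leave Primary 3 and Secondary 2 as planned. At most, report the partial correlation given the day-0 titre, with its 95% confidence interval, as optional support. Do not flag or deselect markers on it.

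Cost: one degree of freedom and a change to the analysis text. If replacing the two tests counts as changing a principal feature, section 9.4 requires a protocol amendment with review by the IRB, the independent safety monitor and NIAID. If day-0 OPA and IgG are not already planned, the cost also includes assaying about 60 elderly day-0 samples, provided that serum is available.

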After identifying the innate immune signatures and correlation immune signatures within each elderly treatment group and each young treatment group, there is an interest in comparing the signatures between PPV23 and PCV13 recipients. Here we consider four groups: elderly PPV23, elderly PCV13, young PPV23 and young PCV13. Each group has two signatures – innate signature and correlation signature. For each group, the correlations signature is a subset of the innate signature. For both the innate and the correlation signature, we will make comparisons between:

A-- the two vaccine groups in the same age category: elderly (60-89) receiving PPV23 v.s. elderly (60-89) receiving PCV13 and young (25-40) receiving PPV23 v.s. young (25-40) receiving PCV13),

B-- all the other possible combinations: elderly (60-89) receiving PPV23 v.s. young (25-40)
receiving PPV23; elderly (60-89) receiving PPV23 v.s. young (25-40) receiving PCV13; elderly (60-89) receiving PCV13 v.s. young (25-40) receiving PPV23; elderly (60-89) receiving PCV13
v.s. young (25-40) receiving PCV13.

This part of the analysis will depend on the results of the aforementioned analysis and hard to specify at this stage.

As a preliminary consideration, the identified innate signature variables and correlation signature variables can be contrasted between groups using descriptive statistics, such tabulation and Venn diagrams.

5. Comparison of generic innate immune responses at days 1, 3 and 7 with adaptive immune responses [Opsonophagocytosis assay OPA titers and ELISA] at years 2-3.5 post vaccination with either PPV23 or PCV13.

For correlation analysis, the analysis is similar to primary endpoint 3. Instead of using all the data, we will analyze data in the elderly.

Enriched biological pathways can be identified using each type of signature in each of the four groups considered above (i.e. elderly (60-89) receiving PPV23, elderly (60-89) receiving PCV13, young (25-40) receiving PPV23 and young (25-40) receiving PCV13), using gene ontology (computer program that generates biological networks from gene lists). Then the enriched pathways can be manually compared between the different treatment groups as per #A and #B above. Biological interpretations of the differences will be made.

9.2.2. Patient populations

For all endpoints, our data analysis will be based on all subjects who are randomized, receive vaccination per label, and for whom there is a blood sample taken at the 2 required time points (Day 0 and Day 30 + 7 - 7 days) and or Day 0 and Day 180.

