In this context, systems biology approaches offer a new approach to compare the global architecture of the immune response between PPV23 and PCV13. Systems biology is a biologybased inter-disciplinary study field that focuses on complex interactions in biological systems, using a new holistic perspective. Systems biology offers several so-called "Omic" technologies that can provide unbiased and rich information on the physiological state of organisms through their molecular profiles. These systems biology approaches are likely to be of value in identifying molecular signatures that are induced rapidly after vaccination and that correlate with, and predict, the later development of protective immune responses. Such a strategy would be particularly useful when evaluating the efficacy or immunogenicity of suboptimal vaccines, or in identifying individuals who are likely to respond sub-optimally to vaccination, such as the elderly receiving PPV23 in particular. Furthermore, the predictive signatures would highlight new correlates of protective immunity and stimulate the formulation and validation of new hypotheses on the biological mechanisms by which such molecular signatures modulate vaccine-induced immunity and protection. Despite this promise in identifying molecular signatures, they have only recently been applied to vaccinology^{10, 11}.

Accordingly, a key goal of the present proposal is to identify molecular signatures that predict the sub-optimal immunogenicity of PPV23 when compared to PCV13 in the elderly. One of the

CONFIDENTIAL

key systems biology technologies that will be employed are microarray analyses. Essentially, blood samples will be isolated at baseline (day 0 prior to vaccination), and at days 1, 3, 7, 14 post vaccination, and the RNA from the peripheral blood mononuclear cells isolated and analyzed for the expression of mRNAs. The microarray platform will be Affymetrix Human Genome U133 Plus 2.0 Array, similar to what we had used previously¹⁰. In our previous work on yellow fever vaccine¹⁰, we identified a gene signature that correlates with and predicted YF-17D CD8+ T cell responses with up to 90% accuracy in an independent, trial. A distinct signature, including B cell growth factor TNFRS17, predicted then neutralizing antibody response with up to 100% accuracy. These findings highlight the utility of system biology approaches in predicting vaccine efficacy.

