9. SAMPLE SIZE CALCULATIONS AND STATISTICAL PLAN

9.1. Sample Size and Power Calculations

The study is explorative. Not enough preliminary data exists to support accurate calculation of the sample size. However we conducted a sample size analysis based on hypothetical scenarios and knowledge of similar studies. Based on previous studies performed at the Hope Clinic and the Vaccine Research Trials Center, the rate of subjects that become ineligible during the study (i.e. do not meet exclusion/inclusion criteria anymore, lost to follow-ups, unable to have blood draws) is between 5 to 10%. Assuming 10% attrition rate, 88 subjects will be recruited and 1:1 randomized into the two treatment groups, resulting in an expected 80 subjects for data analysis. The sample size is on-par with similar studies. In the case that the sample size of subjects missing any of the 4 draws required for the primary endpoint [meaning draws at days 1, 3, 7(\pm 1), and 30 (\pm 7)] is higher than 10% of the 88 subjects to be recruited for the study, we will recruit extra patients to maintain the target sample size of 80 subjects.

The randomization process will be detailed in the MOP. At the center of this study is the identification of generic innate signatures and finding their correlations with the adaptive immune response. The generic innate signatures will be identified from both traditional immune parameters measured by FACS/Luminex assays and array-based gene expression will be measured by microarray experiments. The generic innate signatures will be identified for different treatment groups separately. The traditional immune parameters and array-based gene expression that change after immunization are considered generic innate signatures. The traditional immune parameters and array-based gene expression that change after immunization are considered generic innate signatures. The traditional immune parameters and array-based gene expression that are correlated with the adaptive immune responses (day 30 OPA titers, day 30 IgG levels, day 180 serotype specific avidity indexes, plasmablasts also) are considered correlation signatures of the innate immune responses.

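### Exploratory endpoint 4 names no direct between-vaccine test of innate measures; it contrasts lists selected separately in each arm

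*Combined protocol and SAP*

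**What the plan says.** The aim is comparative. Section 2 (Objectives) states: "We hypothesize that this is due to intrinsic defects in innate responses that could explain the poor immunogenicity of PPV23 when compared to PCV13". Section 1.1 adds that "a key goal of the present proposal is to identify molecular signatures that predict the sub-optimal immunogenicity of PPV23 when compared to PCV13". Exploratory endpoint 3.1.3.4 is the matching endpoint: "Comparison of identified innate signature variables and correlation signature variables between PPV23 and PCV13 recipients".

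The signatures are built within arm. Under primary endpoints 1 and 3 in Section 9.2.1, each elderly vaccine group is analysed by itself. An immune parameter enters the innate signature at p ≤ 0.01 with a mean fold change of at least 3, and a gene enters at FDR ≤ 0.1 by paired SAM. Correlation signatures use p ≤ 0.01 or FDR ≤ 0.1.

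For endpoint 4 the plan says: "This part of the analysis will depend on the results of the aforementioned analysis and hard to specify at this stage". It continues: "As a preliminary consideration, the identified innate signature variables and correlation signature variables can be contrasted between groups using descriptive statistics", giving tabulation and Venn diagrams as examples. A later paragraph, printed under exploratory endpoint 5 but referring back to the group comparisons of endpoint 4, says: "Then the enriched pathways can be manually compared between the different treatment groups as per #A and #B above". It ends: "Biological interpretations of the differences will be made".

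Elsewhere in Section 9.2.1, t-tests or Wilcoxon tests between vaccines are named for IgG, avidity, OPA, plasmablasts, memory B cells, and the plasmablast repertoire and monoclonal antibodies. All of these are adaptive measures.

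**The concern.** A marker can pass the threshold in one arm and just miss it in the other when its true response is the same in both. The difference between significant and not significant is not itself a test of a difference. Null genes admitted by the FDR rule add further one-list entries.

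Because the plan goes on to interpret the differences biologically, chance discordance could be read as a vaccine-specific innate mechanism. The randomised contrast that would address the question is available in the same data: change from day 0 under PPV23 against change from day 0 under PCV13.

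**Working it through.** **Inputs** (Section 9.1): 30 per elderly arm; two-sided paired t-test; design effect 0.66 SD at alpha 0.01 for immune parameters and 0.88 SD at alpha 0.0005 for genes; 80% power stated for both; r = 0.57 at alpha 0.01 for correlations.

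**Step 1. Reproduce the plan's power.** Noncentral t, 29 df, noncentrality d√30. Power is 0.797 at 0.66 SD and 0.798 at 0.88 SD, so the stated 80% reproduces.

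**Step 2. One-list share when both arms have the same true effect.** With within-arm power p and independent arms:
- P(on exactly one list) = 2p(1−p)
- P(on at least one list) = 1−(1−p)²
- Share of detected markers on one list only = 2p(1−p) / [1−(1−p)²]

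At p = 0.797 this is 0.324/0.959 = 0.338.

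| True effect | Alpha | p | One-list share |
|---|---|---|---|
| 0.5 SD | 0.01 | 0.503 | 66% |
| 0.66 SD | 0.01 | 0.797 | 34% |
| 1.0 SD | 0.01 | 0.995 | 1% |
| 0.7 SD | 0.0005 | 0.483 | 68% |
| 0.88 SD | 0.0005 | 0.798 | 34% |
| 1.2 SD | 0.0005 | 0.991 | 2% |

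**Step 3. Lists pooled over days.** The plan does not say whether lists are compared by day or pooled. Suppose a marker changes 0.66 SD on each of days 1, 3 and 7 and is listed if any day passes. With independent days, p = 1−(1−0.797)³ = 0.992 and the share is about 2%. By simulation, a between-day correlation of 0.5 gives about 9% and 0.7 gives about 14%.

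**Step 4. The thresholds actually planned.** The documents give no distribution of effects, so these are ranges under stated assumptions, for one day.
- FDR 0.1 (assumed 20,000 independent genes, 100 to 2,000 truly changed, Benjamini-Hochberg standing in for SAM), truly changed genes only: 27-77% at 0.7 SD, 5-36% at 0.88 SD, 0-2% at 1.2 SD.
- p ≤ 0.01 with mean fold change ≥ 3 (assumed SD of log2 change 0.5 to 1.5): 68-80% when the truth sits exactly at 3-fold, 2-54% at 3.5-fold, 0-28% at 4-fold, 0-4% at 5-fold.
- Correlation test alone at alpha 0.01 (Fisher z): 79% at r = 0.4, 35% at r = 0.57, 5% at r = 0.7. This leaves out the first-stage requirement that a marker already be in the innate signature.

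**Step 5. What a direct test can detect.** Two-sample t, 58 df, noncentrality d/√(2/30). For 80% power it needs 0.91 SD at alpha 0.01 or 1.18 SD at alpha 0.0005. For a difference of 0.66 or 0.88 SD at those alphas, power is 46% or 40%. Under FDR 0.1 with the Step 4 assumptions, and genes changed in one arm only, it finds roughly 2-6% (100 changed genes) to 42% (2,000) at 0.7 SD, and 28-75% at 0.88 SD. For correlations of 0.57 and 0, the Fisher-z difference is 0.648 with standard error √(2/27) = 0.272. The ratio is 2.38, and power at alpha 0.01 is Φ(2.38−2.58), about 42%.

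**The case against.** The strongest reply is that the plan claims little here. Section 9.1 says "The study is explorative", the endpoint is exploratory, the text calls the contrast a preliminary thought, and Section 9.4 reserves other methods, including gene set enrichment. All of that stands. A reader might infer that a between-arm test is ruled out; it is not. None is specified, and Section 9.4 commits to none. The PLSDA mentioned in Section 9.2.1 is for visualising global patterns.

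A reader might also infer that the whole vaccine comparison rests on list overlap. It does not: the adaptive contrast has named tests, and only the innate part lacks one.

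The size of the problem depends on assumptions. It is small for large effects and smaller if days are pooled, and every figure is for single markers. No figure shows how often enriched pathways would disagree, although pathways are a main unit of the planned comparison.

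Finally, a direct test has limited power. That is true, but it is a reason to report intervals. It does not turn list membership into a valid comparison. Nor does the difficulty of specifying the analysis apply to a direct contrast of change, which does not depend on which markers were selected.

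**Conclusion.** The gap is real but limited. The study hypothesis is about innate differences between the vaccines. The endpoint that addresses it names only descriptive contrasts of separately thresholded lists, followed by biological interpretation. At the plan's design effects, about a third of detected markers with no true vaccine difference would appear on one list only. This assumes 30 per arm, independent arms, the sample-size alphas and day-by-day comparison. The share could be near zero for large effects and two thirds for moderate ones.

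It would be wrong to conclude that the primary endpoints are compromised: they are within-arm and unaffected. It would also be wrong to say that a third of reported differences will be false, since that depends on an effect distribution the documents do not give.

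The elderly-young list contrasts are a separate, non-randomised matter. Section 9.2.1 already concedes that the young groups cannot give reliable signatures and points to pathways for that comparison, so they add no weight here. The change should be made because it is cheap and addresses the stated hypothesis directly.

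**What to change.** In exploratory endpoint 4, prespecify for elderly PPV23 vs PCV13, at each of days 1, 3 and 7, a direct comparison of log2 change from day 0:
- **Genes:** two-class unpaired SAM on all array genes, FDR ≤ 0.1.
- **FACS/Luminex:** a two-sample t-test with confidence interval for every parameter at p ≤ 0.01, with the number of tests shown beside the number flagged.
- Restrict neither to markers already in a signature.
- **Correlation signatures:** as a supporting analysis, report the Fisher-z difference between arms with its interval. Use the same log-transformed day 30 OPA measure in both arms, limited to the serotypes common to both vaccines (12, per Section 1.5).
- Keep Venn diagrams and pathway lists as display. Do not call a marker vaccine-specific from list membership alone, and do not report a non-significant contrast as equality.
- Keep elderly-young contrasts at pathway level, as Section 9.2.1 already indicates.

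The cost is a short addition to the plan and a little more analysis of data already collected. Sensitivity is modest (Step 5), so only large differences will be detected reliably and fewer markers are likely to be labelled vaccine-specific.
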